4.5 Data handling

4.5.1 Data management

All primary registration of data will be performed on paper by the ED staff. To ensure a simple procedure for data collection the registration sheet will be present on a specified location in the ED and each section on the sheet marked according to the staff member in charge of each registration. All registration sheets will subsequently be collected by the coordinating investigator and entered online in the REDCap database. Access for data registration and access to already submitted data will be granted to all the initiating investigators.

4.5.2 Confidentiality

All data will be handled in accordance with the act on processing of personal data and no identifiable data will be included in the analysis. When the study is concluded all person-sensitive data will be destroyed.

4.6 Data analysis

4.6.1 Sample size estimation

The number of included patients is calculated using data from an unpublished quality database at Viborg Regional Hospital. Approximately 15 percent of the true Colles' fractures are currently being satisfactorily reduced, and we consider an increase to 30 percent to be clinically relevant. With $\alpha = 0.05$ and $\beta = 0.8$, 121 patients are needed in each group to detect a statistically significant difference in reduction satisfaction. From the same local database we found that the true Colles' fracture comprises approximately 90 % of the total number of fractures and we anticipate a total inclusion of 268 patients ($2 \times 121 + 10\%$).

4.6.2 Statistics

Binary data, including primary endpoint will be analysed using chi squared test. For normally distributed measurements the differences between groups will be compared using Student's *t*-test. Variables considered not to be normally distributed will be analysed by Mann-Whitney's *U*-test. Two-tailed *P*-values < 0.05 will be considered statistically significant.

5. Ethical concerns

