4.2 Randomisation

4.2.1 General considerations

Participants will be randomized in either the intervention or the control group using the online randomization tool Research Electronic Data Capture (REDCap, Aarhus University, Denmark).

All patients will receive an intravenous access. Monitoring of heart rate, blood pressure and oxygen saturation will be established according to local guidelines at each inclusion site before injection of local anaesthetic.

In both groups, the reduction process will begin 10 minutes after the block has been performed. The technique for the actual reduction may vary amongst physicians. To best reflect the clinical practices and to avoid the risk of an insufficient reduction due to the physician being forced to comply to a technique unfamiliar to him, no further standardisation will be made in this regard.

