4.2.3 Control group

Patients in the control group will receive the standard haematoma block at all inclusion sites. This will be performed using the previously described technique and local anaesthetics according to local practices.

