4.4 Data collection

In both groups, the following will be registered during the treatment period in the emergency department:

- Pain scores using an 11-step numeric rating scale (NRS) ranging from 0 (no pain) to 10 (worst pain imaginable)
 - Before local anaesthetics are given
 - During the local anaesthetic procedure
 - During reduction
- Precise amount and type of local anaesthesia used
- In plane/out of plane technique used for the ultrasound guided blocks
- Type and amount of supplementary analgesics/sedatives before and after local anaesthesia
- Fracture classification code
- Treatment plan; conservative vs. operation
- Osteoporosis yes/no
- Patients right/left hand preference
- Patient height and weight
- Any chronic use of opioids

Following casting of the fracture a control X-ray will be performed and subsequently evaluated independently by two skilled orthopaedic surgeons to establish if the reduction was satisfactory. In case of disputes a third orthopaedic surgeon will evaluate the X-ray and make a final ruling. The orthopaedic surgeons will further determine fracture type.

In cases where more than one control X-ray is performed due to re-manipulation of the fracture, only the first will be evaluated. The fracture will be deemed satisfactory using a binary outcome measure (yes/no) if all the following requirements set by the National Clinical Guideline for Treatment of Distal Radius Fractures(14) are met:

- < 10-degree dorsal angulation of the radial articular surface
- Ulnar variance < 2 mm
- Discontinuation of the articular line < 2 mm
- No incongruence of the distal radioulnar joint

Two months after the initial treatment the electronic journal will be evaluated to establish the occurrence of secondary dislocation and need for surgery.

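### The primary chi-squared test is valid and correctly powered, but it uses neither site nor available baseline variables; a pre-specified adjusted analysis may add precision at almost no cost.

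*Combined protocol and SAP*

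**What the plan says.** - **Primary test (4.6.2 Statistics).** "Binary data, including primary endpoint will be analysed using chi squared test", judged two-sided at the 5% level. No adjusted or stratified analysis is given, either as primary or as sensitivity.
- **Allocation (4.2.1 General considerations).** "Participants will be randomized in either the intervention or the control group" through REDCap. No stratification factor is named.
- **Control block (4.2.3 Control group).** All sites give the standard haematoma block, with "local anaesthetics according to local practices". Section 2.2 describes both a blind and an X-ray-guided technique. Section 4.2.1 deliberately leaves the reduction technique to the physician.
- **Baseline data (4.4 Data collection).** The sheet includes "Osteoporosis yes/no", but the analysis gives it no role. Age appears as an eligibility criterion in 4.1.2. Neither age nor site is on the 4.4 list, though both must be known.
- **Sample size (4.6.1).** "Approximately 15 percent of the true Colles' fractures are currently being satisfactorily reduced", and "we consider an increase to 30 percent to be clinically relevant". This leads to 121 per group and a total of 268.

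**The concern.** In a multi-site trial with a binary outcome, the chance of success may depend on where the patient is treated and on patient characteristics. A test that ignores such variables is valid, but it can be less powerful than one that uses them. The protocol leaves room for site differences in the control block, and its planning rate comes from a single hospital's database, so rates elsewhere are unknown.

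The sample size has no cushion. The inflation to 268 covers only fractures that are not true Colles': 268 × 0.90 = 241, against 2 × 121 = 242 needed. Nothing is set aside for withdrawals or missing control X-rays. Precision obtainable from data already known is therefore worth having. What is at stake is a few points of power, not the validity of the result.

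**Working it through.** **1. Reproduce the plan's figure.** Inputs from 4.6.1 and 4.6.2: p1 = 0.15, p2 = 0.30, two-sided alpha 0.05, power 0.80 (printed as beta = 0.8; the result of 121 confirms that power is meant).

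n per group = [1.960 × √(2 × 0.225 × 0.775) + 0.842 × √(0.15 × 0.85 + 0.30 × 0.70)]² / 0.15²

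= [1.960 × 0.5906 + 0.842 × 0.5810]² / 0.0225 = 120.5, rounded up to **121**.

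Power at 121 = Φ[(0.15 × √121 − 1.960 × 0.5906) / 0.5810] = Φ(0.848) = **80.2%**. The trial is correctly sized for the test it names.

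**2. Approximate gain from adjustment.** If the adjusting variables explain a fraction R² of the outcome variance, the effective n per arm is about 121/(1 − R²). R² is not in the documents, so a range is assumed.

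| R² | Effective n per arm | Power | n per arm for 80% power |
|---|---|---|---|
| 0 | 121.0 | 80.2% | 121 |
| 0.02 | 123.5 | 81.0% | 119 |
| 0.05 | 127.4 | 82.2% | 115 |
| 0.10 | 134.4 | 84.2% | 109 |
| 0.20 | 151.2 | 88.2% | 97 |

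**3. Simulation with the same data for every test.** There were 3,000 trials per scenario, 121 per arm, four sites (assumed; the text available gives no number), allocation not stratified, and overall rates held at 15% and 30%. A site SD of 0.5 log-odds corresponds to control rates of about 8% to 24% across sites, and an SD of 1.0 to about 3% to 33%. The Monte Carlo SE of one power figure is √(0.8 × 0.2/3000) = 0.7 points.

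| Site SD | Covariate log-odds per SD | Chi-squared | CMH by site | Logistic, site + covariate (Wald) | Logistic minus chi-squared, points |
|---|---|---|---|---|---|
| 0 | 0 | 80.8% | 80.2% | 79.9% | −0.9 |
| 0 | 0.5 | 80.5% | 80.1% | 81.8% | 1.3 |
| 0 | 1.0 | 81.1% | 80.2% | 85.2% | 4.1 |
| 0.5 | 0 | 79.4% | 80.1% | 80.2% | 0.8 |
| 0.5 | 0.5 | 80.9% | 81.6% | 83.1% | 2.2 |
| 0.5 | 1.0 | 80.2% | 81.1% | 86.1% | 5.9 |
| 1.0 | 0 | 80.9% | 86.0% | 86.1% | 5.2 |
| 1.0 | 0.5 | 80.1% | 84.9% | 86.0% | 5.9 |
| 1.0 | 1.0 | 80.2% | 83.8% | 88.6% | 8.4 |

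At a site SD of 0.5, stratifying by site alone (Cochran-Mantel-Haenszel, CMH) gains 0.7 to 0.9 points. At 1.0 it gains 3.6 to 5.1. Type I error was 4.9% for chi-squared, 4.3 to 4.8% for CMH and 4.4 to 4.5% for the logistic Wald test.

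**4. Smaller, named effects.** With site-stratified allocation for all tests, site SD 0.3 to 0.5, osteoporosis odds ratio 1.5 and age odds ratio 1.2 per SD (all assumed), power was 80.4 to 80.6% unadjusted and 82.1 to 82.6% adjusted. With odds ratios of 2.0 and 1.4 it was 80.8% and 83.8%.

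**5. The estimator proposed below.** Simulating the standardised risk difference itself gave gains of about 0 points with no prognostic effect, 1 to 3 with modest effects and 5 to 7 with strong ones. Its type I error was 4.8 to 5.9%. A likelihood-ratio test is less safe: in one set of 1,500 trials per scenario its type I error ran from 4.4% to 6.9%. The upper figure is (6.9 − 5.0)/0.56 = 3.4 Monte Carlo SEs above 5%, where 0.56 = 100 × √(0.05 × 0.95/1500).

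**6. Can the model be fitted?** Expected events are 121 × 0.15 + 121 × 0.30 = 18 + 36 = 54. With four sites the model has six coefficients besides the intercept (arm, three for site, age, osteoporosis), so about 54/6 = 9 events each. That is workable if small sites are pooled.

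**The case against.** The strongest reply is that nothing here is wrong. The chi-squared test is valid under randomisation, holds its type I error, matches the sample size exactly and leaves the analyst no freedom. All of that stands, and it rules out several stronger readings that a reader might infer.

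- *That the control block differs by site.* Section 4.2.3 gives the standard block everywhere and leaves the agents to local practice. That permits differences but does not show them. Differences in the block would in any case bear mainly on whether the treatment effect varies by site. They yield precision only if site also predicts the outcome.
- *That varying reduction technique is a site effect.* Section 4.2.1 attributes it to physicians, so a site term may not capture it.
- *That precision is definitely lost.* No document says that site, age or osteoporosis predicts satisfactory reduction.
- *That chance site imbalance biases the result.* It is ordinary sampling error, already reflected in the test. Under simple allocation it moved the risk difference by an SD of 0.8 points (control rates 8 to 24%) to 1.5 points (3 to 33%), against a 15-point target.

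A further objection is that a model with about nine events per coefficient, and loose rules for sparse sites, could allow the primary method to be chosen after the data are seen. This is fair against a loosely written remedy. It is met by fixing one estimator, a short covariate list and a pooling rule in advance.

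**Conclusion.** The point holds as an efficiency improvement, not as an error. The planned test is sound and correctly powered, but it leaves unused some variables that are already available. The likely gain is about 0 points of power if site, age and osteoporosis are not prognostic, 1 to 3 if modestly so and 5 to 7 if strongly so. The logistic Wald test reached 8.4 only in the most extreme scenario. Site alone contributes about 1 point or less unless site rates differ widely. These sizes rest on an assumed four sites and on assumed prognostic strengths, neither of which the documents supply.

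The text needs completing whichever way REDCap is configured. If allocation is in fact stratified by site, an unadjusted test is slightly conservative when sites differ, which strengthens the case for adjustment. Label: cheap improvement.

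**What to change.** Before any outcome data are seen, amend 4.6.2 as follows:

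- Name one primary analysis: a logistic model of satisfactory reduction (true Colles' fractures) on arm, site, age and osteoporosis. Predict each patient's probability under each arm, average over all patients and take the difference. Report this standardised risk difference with a robust Wald-type 95% confidence interval and p-value, not a likelihood-ratio test.
- State the rule for pooling small sites, for example combining those below a fixed number of true Colles' fractures. Leave no data-driven choice between methods.
- Keep the chi-squared test as a sensitivity analysis and leave N unchanged.
- Add age and site to the items listed in 4.4.
- If the allocation can still be set, stratify it by site in REDCap and say so in 4.2.1. If it is already stratified, say that.

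The cost is a paragraph of text, possibly one REDCap setting and a little more analysis work. The drawbacks are that small sites must be pooled and that nothing is gained if the covariates turn out not to be prognostic.

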3.1 Hypothesis

We hypothesize that ultrasound guided blocking of the radial and median nerves will improve fracture reduction satisfaction for the true Colles' fractures and improve analgesia for reduction of all fracture types compared to the standard haematoma block.

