3.3 Secondary outcomes

Will be evaluated for all included fracture types.

- Pain scores using an 11-step numeric rating scale
- Time spent in the Emergency Department
- Secondary fracture dislocation

4 Study design and conduction

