4.1 Selection and enrolment of participants

4.1.1 Recruitment strategy and screening

Patients eligible for screening for inclusion are identified in the Emergency Department (ED) at all recruitment sites upon primary contact. When an X-ray has revealed the relevant fracture, the ED-staff will call the available anaesthesiologist or anaesthesiologist trainee who will perform the inclusion process and randomisation. In cases where the anaesthesiologist is unable to perform inclusion due to e.g. lack of time or experience a registration of patient data, date and time as well as the reason for the missed inclusion will be made.

In case of randomisation to the control group, the anaesthesiologist/anaesthesiologist trainee will leave the ED and take no further part in the treatment or data registration. In case of randomisation to the intervention group the anaesthesiologist/anaesthesiologist trainee will perform the ultrasound guided blocks and leave the ED before the reduction procedure begins.

For all included patients a note will be made in the electronic patient journal stating that the patient meets all in- and no exclusion criteria, has given an informed consent to participation and received a copy of the signed consent form.

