4.3 Blinding

Only the orthopaedic surgeons evaluating the control X-ray to assess the primary outcome of fracture reduction satisfaction will be blinded to randomisation.

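### Pain scores are to be compared without adjusting for the recorded pre-block score, which gives up some precision but not validity

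*Combined protocol and SAP*

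**What the plan says.** The second half of the hypothesis (3.1) is that the nerve blocks will "improve analgesia for reduction of all fracture types". The outcome that measures this is the first secondary outcome in 3.3, "Pain scores using an 11-step numeric rating scale", evaluated for all fracture types.

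Section 4.4 collects the score three times in both arms: "Before local anaesthetics are given", during the block, and during reduction. It also collects "Type and amount of supplementary analgesics/sedatives before and after local anaesthesia".

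Section 4.6.2 is the whole statistical plan. It gives chi-squared for binary data. For continuous data it says "For normally distributed measurements the differences between groups will be compared using Student's" t-test, with Mann-Whitney for variables judged non-normal. No covariate, change score or regression model appears in any section, so the pre-block score has no stated role in the analysis.

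Three further statements bear on whether that score is a true baseline. The anaesthesiologist called to the emergency department is the one "who will perform the inclusion process and randomisation" (4.1.1). "All primary registration of data will be performed on paper by the ED staff" (4.5.1). "Only the orthopaedic surgeons evaluating the control X-ray to assess the primary outcome" are to be blinded (4.3).

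**The concern.** If pain before the block predicts pain during reduction, part of the between-patient spread in the outcome can be explained by a value the trial already holds. Leaving it out makes the confidence interval for the pain difference wider than the data require. Sample size was set for the binary primary outcome only, so nothing in the plan shows how precise the pain comparison will be.

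Two things limit the concern. The correlation may be low, because the outcome is pain after a block and some patients will also have had analgesics or sedatives. And the pre-block score is not yet a secure covariate: its only timing rule is that it precedes the local anaesthetic, so unblinded staff could score it once the arm is known.

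**Working it through.** **Inputs from the documents.** Two-sided alpha 0.05 (4.6.2); 15% against 30%, 121 per group and 268 in total (4.6.1). The plan writes beta = 0.8; it is read here as power 0.80, because that reproduces its figure.

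**The plan's own figure.** Pooled formula for two proportions, mean rate 0.225:

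n = [1.96·√(2·0.225·0.775) + 0.842·√(0.15·0.85 + 0.30·0.70)]² / 0.15² = (1.157 + 0.489)² / 0.0225 ≈ 120.5, so 121 per group.

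The total of 268 lies between 242 × 1.1 = 266.2 and 242 / 0.9 = 268.9. With equal allocation, which 4.6.1 implies, that is 134 per arm for an outcome covering all fracture types.

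**Assumed, because the documents do not give them.** NRS SD of 2, 2.5 or 3; a true difference of 1 point; correlation ρ between the pre-block score and the later score of 0.1 to 0.6.

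**Formulas.** Unadjusted SE = SD·√(2/134). ANCOVA multiplies it by √(1 − ρ²). Power = Φ(1/SE − 1.96). CI half-width = 1.96·SE.

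At SD 3 the unadjusted SE is 3 × 0.1222 = 0.367.

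| ρ | SE ratio | Half-width, SD 3 | Power, SD 3 | Power, SD 2.5 |
|---|---|---|---|---|
| unadjusted | 1 | 0.72 | 78% | 91% |
| 0.1 | 0.995 | 0.71 | 78% | 91% |
| 0.2 | 0.980 | 0.70 | 80% | 92% |
| 0.3 | 0.954 | 0.69 | 82% | 93% |
| 0.5 | 0.866 | 0.62 | 88% | 97% |
| 0.6 | 0.800 | 0.57 | 93% | 98% |

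At SD 2 the unadjusted power is already 98%.

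**Does this survive a bounded integer scale?** Simulation with 134 per arm, mean 5, SD 3 and a shift of 1, rounded and clipped to 0–10 (realised SD 2.74, difference about 0.90; 4,000 runs per setting):

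- t-test: 75–77%
- Mann-Whitney: 74–76%
- ANCOVA: 78%, 78%, 79%, 87% and 91% at ρ 0.1, 0.2, 0.3, 0.5 and 0.6

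With no true difference (8,000 runs each), all three tests rejected in 5.0–5.5% of runs. A separate simulation at SD 2.5 with a shift of 0.86 gave ANCOVA 82%, 88% and 92% at ρ 0.3, 0.5 and 0.6, against about 79–80% for the t-test.

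**What if the pre-block score is taken after allocation is known?** Suppose this shifts it by s points in one arm. With equal SDs the ANCOVA estimate then moves by about ρ·s: for s = 0.5 and ρ = 0.5, by 0.25 points. At SD 3 the mean squared error would be 0.134 × 0.75 + 0.25² = 0.101 + 0.0625 = 0.163, against 0.134 unadjusted. The variance saved is ρ²·SE² and the squared bias is ρ²·s², so adjustment stops paying once s exceeds the unadjusted SE, here 0.367 points, whatever ρ is.

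**The case against.** The strongest reply is that nothing here is an error. Unadjusted tests on a secondary outcome are legitimate, and the size of the loss is assumed throughout. A useful gain in power needs an SD near 3 and a correlation of at least 0.3, and nothing in the documents supports either. At SD 2.5 and ρ 0.3 the half-width moves only from 0.60 to 0.57.

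An effective block may also push many scores to zero, where Mann-Whitney, already in the plan, does well. With 53–59% zeros in the intervention arm (3,000 runs), Mann-Whitney gave 81–84% power and ANCOVA 80–83% at ρ 0.1. They were within 1 point of each other at ρ 0.2, ANCOVA led by under 2 points at ρ 0.3, and it led by about 6 points at ρ 0.5.

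Finally, the covariate is insecure as the protocol stands, and securing it means a workflow rule across sites with many enrolling physicians (1.4), where one person randomises and others record.

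Most of this stands as a limit on size. It does not remove the point. With a strong floor, ANCOVA was at worst about 1–2 points below Mann-Whitney at ρ 0.1 or less, while the gain at higher correlations is real. The insecure baseline is a reason to fix its timing, with the unadjusted test as fallback.

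**Conclusion.** The concern holds, as a loss of precision and not of validity. The plan collects a pre-block pain score and assigns it no use in the comparison that tests its analgesia hypothesis. The primary outcome, the sample size and the type I error are untouched.

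The loss cannot be fixed from the documents. On the assumptions above, adjustment narrows the interval by 0.5% at ρ 0.1, 2% at 0.2, 5% at 0.3, 13% at 0.5 and 20% at 0.6. It matters for power from about ρ 0.3 if the SD is near 3, and hardly at all at ρ 0.2 or below or at SD 2. That the analysis is unadjusted is inferred from the tests named; the plan does not expressly rule adjustment out. The recommendation rests on the pre-block score being taken before allocation is known.

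**What to change.** **In 4.6.2:** analyse NRS by ANCOVA with arm and pre-block NRS, and report the adjusted mean difference with its 95% CI. Keep Mann-Whitney as a sensitivity analysis. The model needs a named outcome, and the plan does not rank the two later scores, so state that NRS during reduction is the main pain outcome and NRS during the block the next. Replace a missing pre-block score with the mean of both arms pooled, so that no patient drops out of the analysis.

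**In 4.4:** state that the pre-block NRS is recorded before randomisation and is used only as a covariate. If this cannot be assured, keep the unadjusted comparison as the main analysis.

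**Cost:** one analysis sentence, one degree of freedom, a missing-baseline rule, and a fixed step at every site (score pain, then open the randomisation tool), which the formal introduction of enrolling physicians in 1.4 could cover. No new data item and no extra patients. The change should be made before any outcome data are seen, since a covariate added later would look data-driven.

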5.1 Approvals

Permission for conduction of the study and gathering of information in the electronic patient journal will be received from the Ethical Committee and the Danish Data Protection Agency through the common Regional system in the Central Denmark Region.

We specifically seek permission to access all relevant journal entries in the participants electronic journal regarding the current forearm fracture and its treatment from the point of primary contact to the ED and for the remainder of the study period. This includes any X-ray information available in different electronic systems.

